### **5.7.3 Rescue Medications**

Lorazepam (a benzodiazepine) may be used as a rescue medication for the management of agitation and/or aggression. Any use or increase in dose of lorazepam will be documented as a rescue medication, even if given to subjects for symptoms other than agitation and aggression. Lorazepam at a maximum dose of up to 2 mg per 24-hour period will be allowed as rescue medication on an intermittent or PRN basis only, and should not be taken within 24 hours prior to the next study visit. Lorazepam may not be used for more than 10 cumulative days after randomization in any 4-week period. If lorazepam is not available, another intermediate acting benzodiazepine may be used at doses equivalent to lorazepam doses.

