## 5. Anxiolytics and sedative medications:

- Use of anxiolytic medications (including benzodiazepine) is restricted. The dose of these medications must be unchanged for at least 4 weeks prior to Baseline and should be expected to remain unchanged until the subject's final visit.
- Exception: lorazepam (a benzodiazepine) may be used as a rescue medication for the management of agitation and/or aggression per [Section 5.7.3](#). If lorazepam is not available, another intermediate-acting benzodiazepine may be used in the same way lorazepam may be used at doses equivalent to lorazepam doses.
- Use of sedative insomnia aids is permitted PRN with restrictions as noted in the list of prohibited and restricted medications.

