The change from Baseline to Week 12 in the ADCS-ADL and NPI-C total score, combined delusions and hallucinations, combined dysphoria and apathy/indifference and individual domain scores (except the agitation and aggression domains) will be summarized using an analysis of covariance (ANCOVA) model with effects for treatment group (pimavanserin 34 mg, pimavanserin 20 mg, or placebo) and geographic region (North America, Europe, or Rest of World) as factors, and the Baseline value of the endpoint being summarized as a covariate. Missing values will be imputed with the previous value (including Baseline) for

that subject, i.e. last observation carried forward (LOCF). In addition, an observed-case summary, ignoring missing values, will also be presented.

At Week 12, the effect size (Cohen's d) for the change from Baseline between the treatment groups (each pimavanserin group versus placebo group) will be calculated using the following formula:

$$\text{Effect size} = \frac{\text{LS mean difference}}{\sqrt{\text{MSE}}}$$

Where MSE is the mean squared error from the ANCOVA model. The sign (+ or -) of the effect size will be chosen so that an effect size favoring pimavanserin will be reported as a positive number and an effect size favoring placebo will be reported as a negative number.

The change from Baseline to each post-Baseline timepoint (Weeks 4, 8 and 12) in the MMSE will be summarized using an MMRM model in Full Analysis Set similar to that described above for the primary endpoint in [Section 13.1](#), except that the Baseline value of the MMSE will be included in the model instead of the Baseline CMAI total score. Also, the MMSE is not measured at Week 2.

Results will be presented in summary table similar to the outputs described in Section 13.1.

The use of rescue medication is determined from the Rescue Medications eCRF. The proportion of subjects taking any rescue medication during the treatment period for the Full Analysis Set will be summarized by treatment group.

Correlations among efficacy endpoints (observed cases) at Baseline (combining all 3 treatment groups) and for change from Baseline at Week 12 (combining all 3 treatment groups and by treatment group) will be assessed using Spearman's rank correlation coefficient (Spearman's rho) and presented in a correlation matrix. The 95% CIs for the Spearman's rank correlation coefficients will also be presented.

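### Protocol 5.7.3 and Appendix C item 5 conflict for stable daily lorazepam, which, read literally, also counts as rescue use in the exploratory rescue proportion

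*Protocol*

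**What the plan says.** Appendix C item 5 of the protocol sets the background rule: "Use of anxiolytic medications (including benzodiazepine) is restricted". The condition is stability: "The dose of these medications must be unchanged for at least 4 weeks prior to Baseline", with no change expected up to the final visit. The same item then adds an exception allowing lorazepam as rescue medication under Section 5.7.3. It does not say that stable background lorazepam is barred.

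Protocol 5.7.3 sets the rescue rule. "Any use or increase in dose of lorazepam will be documented as a rescue medication", and this applies even when the drug is given for symptoms other than agitation and aggression. Lorazepam "will be allowed as rescue medication on an intermittent or PRN basis only". There is also a pre-visit limit: the drug "should not be taken within 24 hours prior to the next study visit". A separate sentence limits the number of days: "Lorazepam may not be used for more than 10 cumulative days after randomization in any 4-week period". A substitute is conditional: "If lorazepam is not available, another intermediate acting benzodiazepine may be used at doses equivalent to lorazepam doses".

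The proportion of subjects taking any rescue medication over the 12 weeks is an exploratory endpoint (Protocol 2.3.2.1). SAP 13.3 gives its source: "The use of rescue medication is determined from the Rescue Medications eCRF". Neither SAP 13.3 nor SAP 11 has a rule that separates background from rescue lorazepam.

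**The concern.** For a subject who enters the trial on scheduled daily lorazepam, the two protocol passages give opposite answers. Appendix C asks for the dose to stay the same. Section 5.7.3 sets a day limit that the same dosing must exceed.

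Two things are at stake. The first is the rescue endpoint. A subject whose lorazepam pre-dates randomization would be counted as rescued from Day 1 whatever the study drug does, so the proportion would mix existing treatment with new need. The second is deviation status. The text does not settle whether such a subject has deviated. SAP 4 removes from the Per-protocol set subjects with deviations judged to have substantial impact on the CMAI outcome, and SAP 13.1 and 13.2 repeat the CMAI and ZBI models in that set.

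**Working it through.** The plan gives no figure to reproduce. The check applies each rule to each type of user, then follows the result to the endpoint.

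**1. Scheduled daily lorazepam, dose unchanged since at least 4 weeks before Baseline**
- Appendix C item 5: satisfied.
- 10-day limit in 5.7.3: counting Day 1 as the first day, cumulative use on Day d is d days, so the limit of 10 is passed on Day 11. In one 4-week period, use is 28 days against 10. Over the treatment period it is 12 × 7 = 84 days, against at most 3 × 10 = 30 over three consecutive 4-week periods.
- 24-hour limit in 5.7.3: daily intake also falls within the 24 hours before a clinic visit.
- Documentation rule in 5.7.3: on its literal words, this is use of lorazepam and is recorded as rescue.

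The PRN and 24-hour limits are attached to lorazepam given as rescue. The 10-day sentence is worded for lorazepam itself, so it applies however the use is labelled.

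**2. Other users**
- Intermittent background lorazepam, on 10 days or fewer in any 4 weeks and none within 24 hours before a visit: breaks no limit, but is still documented as rescue.
- Stable use of another benzodiazepine: 5.7.3 does not reach it, unless it is the substitute for unavailable lorazepam. It breaks nothing there and does not count as rescue.

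**3. Trace to the endpoint**

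Section 5.7.3 decides what is documented as rescue, SAP 13.3 reads the Rescue Medications eCRF, and the summary counts any use. No step in between removes unchanged background lorazepam.

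**4. Illustration only**

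The documents give neither a background lorazepam rate nor a rescue rate. Let q be the share of an arm on background lorazepam and r the rescue rate among the others, both assumed.

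Reported proportion = q + (1 − q) × r

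- q = 5%, r = 10%: 0.05 + 0.95 × 0.10 = 14.5%
- q = 15%, r = 20%: 0.15 + 0.85 × 0.20 = 32.0%
- q = 5%, r = 30%: 0.05 + 0.95 × 0.30 = 33.5%
- q = 15%, r = 30%: 0.15 + 0.85 × 0.30 = 40.5%

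If q is equal in two arms, the reported difference is (1 − q) times the difference among the others, so it shrinks by 5% to 15% over this range of q.

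The effect on precision uses 111 / 3 = 37 per arm and SE of the arm difference = √(2p(1 − p)/37), with p the same in both arms:

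- p = 30%: 10.7 points
- p = 33.5%: 11.0 points
- p = 40.5%: 11.4 points

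The net rise is therefore about 0.3 to 0.8 points.

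**The case against.** The strongest reply is that the text allows softer readings.

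- The word exception in Appendix C could move lorazepam wholly under 5.7.3, so that the stable-dose rule never covers it. This is possible but not stated; the sentence only adds a permitted rescue use.
- If any use already included unchanged background dosing, the reference to an increase in dose would be redundant. The phrase could therefore mean new use, or an increase over an existing dose. On that reading the stable user is not documented as rescued and the endpoint problem disappears. The 10-day conflict remains.

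Parts of the reply stand. The eCRF completion instructions and the Study Deviation Rules Document cited in SAP 7 are not available here and may settle the classification. Sites can also take questions on restricted medications to the Medical Monitor (Protocol 5.7.2), so it would be wrong to say that they have no recourse. Concomitant medications are summarized under SAP 11 and all data are listed under SAP 5, so background use can be found afterwards.

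A reader might infer that every background benzodiazepine user is caught. The documents do not support this, because 5.7.3 names lorazepam and a conditional substitute only. A reader might also infer a large loss of precision from chance imbalance in background use between arms. Even with the assumed rates, the net rise in the standard error is under 1 point on a base of nearly 11.

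**Conclusion.** The inconsistency is real and narrow. A subject on stable scheduled daily lorazepam meets Appendix C item 5, breaks the day limit in 5.7.3 from Day 11, and on the literal text enters the rescue proportion. Intermittent lorazepam users within the limits break no limit but are still documented as rescued.

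The consequence is confined to one exploratory endpoint, summarized descriptively with no hypothesis testing, and to deviation and possibly Per-protocol classification. The primary CMAI model in the Full Analysis Set is not touched. The size of the effect cannot be derived from the documents; the percentages above rest on assumed rates and show only direction and form. The endpoint part of the conclusion also assumes that the eCRF is completed as 5.7.3 literally directs.

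**What to change.** Protocol 5.7.3 and Appendix C item 5 must be reconciled so that the status of stable scheduled lorazepam is stated once. This review takes no position on which clinical rule should stand.

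In SAP 13.3, add a classification sentence for the rescue proportion:

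- Unchanged scheduled lorazepam that pre-dates Baseline is left out of the rescue count and tabulated separately by treatment group. The subject stays in the denominator.
- New use, a dose increase, and any PRN or intermittent use of lorazepam or its substitute after first dose still count as rescue, including PRN use first begun before Baseline.

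The last clause is needed. A rule keyed only to use started or increased after first dose would miss a subject who began PRN lorazepam before Baseline and took it at the same dose for agitation after randomization.

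The cost is small: one SAP sentence and a check against medication records, which Protocol 5.7 already requires from up to 12 weeks before Baseline. Timing allows it. The last subject was randomized on 2 November 2017, so Week 12 (Day 85, 84 days later) falls on 25 January 2018, after the SAP date of 29 November 2017. The protocol clarification can guide only subjects still on treatment, but the SAP rule can cover all 111.

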## **5.8 Blinding**

Treatment assignment will be double-blind where neither the subjects, study partners/caregivers, Sponsor personnel who oversee the study, nor the Investigator and study personnel will know which treatment is assigned to each subject. See [Section 7.10](#) for details regarding medical emergency unblinding procedures.

## **5.9 Investigational Drug Handling**

### **5.9.1 Test Article**

Pimavanserin tartrate is a white to off-white powder. Pimavanserin tablets include the active compound (pimavanserin) and the following excipients: [REDACTED]

Placebo tablets contain all of the same excipients as pimavanserin 10 mg and 17 mg tablets except for the active compound.

Pimavanserin and placebo used for the tablets are manufactured under current Good Manufacturing Practices compliance by [REDACTED]

### **5.9.2 Investigational Drug Packaging**

Pimavanserin will be provided as 10 mg and 17 mg strength tablets; matching placebo tablets will also be provided. ACADIA or its designee will supply the pimavanserin and placebo tablets.

During the treatment period, study drug will be supplied in kits which will contain 4 blister cards; each kit is sufficient for a 4-week supply. Each blister card contains 20 tablets. Each blister card contains study drug for 10 days.

### **5.9.3 Receipt of Investigational Drug Supplies**

The Investigator and/or study staff is responsible for taking an inventory of each shipment of investigational drug received and comparing it with the accompanying drug accountability report/material shipping form. The Investigator or study staff member will verify the accuracy of the information on the form, sign and date it, and provide a copy of the form to the Sponsor or designee. All investigational drug supplied is for use in this study only and should not be used for any other purpose.

### **5.9.4 Storage of Investigational Drug**

The investigational drug must be kept at 15°C to 30°C (59°F to 86°F) [see USP Controlled Room Temperature] in a secure area with restricted access and according to applicable country, state, and federal regulations. Neither the Investigator, nor the pharmacist, nor any of his/her designees may provide investigational drug to any person not participating in the study.

### **5.9.5    Investigational Drug Dosing**

The first dose of study drug will be administered at the clinic; study drug kits will then be dispensed to the subject to take home. It is recommended that the subject take the study drug at approximately the same time each day until the Week 12 (EOS/ET) visit. Each daily dose consists of 2 individual tablets that should be taken together. Study drug can be taken with or without food consumption.

#### **5.9.5.1    Treatment Period**

At Baseline (Day 1), subjects will be randomized to double-blind study treatment and take their first dose from a new drug kit while at the clinic, and will be provided with the drug kit to take home. Study personnel will dispense study drug to subjects by accessing the IXRS.

Additional kits will be provided at Week 4 and Week 8 clinic visits. Investigational drug supplies will be labeled in accordance with all applicable guidelines and/or regulations and will be blinded as to subject treatment assignment.

#### **5.9.6    Record of Dispensing**

Accurate recording of all investigational drug administration for individual subjects will be made in the appropriate section of the subject's eCRF as well as in the site investigational drug dispensing and reconciliation form. Drug accountability records must be updated as subjects are enrolled and throughout the conduct of the study.

#### **5.9.7    Accountability**

The Investigator or designee will keep current and accurate records of the investigational drug product dispensed, used, and returned for each subject to assure the health authority and Sponsor that the investigational drug is being handled appropriately. Subjects should be instructed to return all used/empty kits, blister cards and unused tablets to the Investigator at regularly scheduled clinic visits and at the EOS/ET visit.

At appropriate intervals during the study, investigational drug reconciliation will be performed by the Sponsor representative who may return appropriate used and unused investigational drug and used and unused packaging to the Sponsor's designee for destruction.

At the conclusion of the study, final investigational drug reconciliation will be conducted at the site. Final investigational drug accountability documentation will be maintained at both the site and at ACADIA. Any remaining unused investigational drug and all used and unused packaging will be sent back to the Sponsor's designee for destruction. Documentation of investigational drug destruction will be recorded and maintained by both ACADIA and the Sponsor's designee.

## **6 EFFICACY, SAFETY, AND PHARMACOKINETIC ASSESSMENTS**

### **6.1 Efficacy Assessments**

The following efficacy endpoints will be assessed in this study using the measures described in this section: Cohen-Mansfield Agitation Inventory (CMAI), Zarit Burden Interview (ZBI), Neuropsychiatric Inventory–Clinician Rating Scale (NPI-C), Mini-Mental State Examination (MMSE), modified Alzheimer’s Disease Cooperative Study–Clinical Global Impression of Change (mADCS-CGIC), Karolinska Sleepiness Scale (KSS), and Alzheimer’s Disease Cooperative Study–Activities of Daily Living Inventory (ADCS-ADL).

Of the measures listed in the following sections, the CMAI should be completed first, followed by completion of the other instruments. For each scale, the time period assessed will be from the time of the last scheduled assessment (e.g., Baseline visit to Week 2, Week 2 to Week 4, Week 4 to Week 8, and so on).

#### **6.1.1 Cohen-Mansfield Agitation Inventory (CMAI)**

The CMAI was developed to assess the frequency of manifestations of agitated behaviors in elderly persons ([Cohen-Mansfield 1989](#); see [Appendix E](#)).

The CMAI is a 29-item scale designed to systematically assess agitation, rated on a 7-point (1-7) scale of frequency. Subjects are rated by their primary caregiver regarding the frequency with which they manifest physically aggressive, physically non-aggressive, and verbally agitated behaviors. The CMAI in this study is to be completed by interview of the caregiver. Ratings are inclusive of the 2 weeks prior to the administration of the scale.

Separate scores for agitation and aggression behaviors can be derived from the CMAI in addition to the total score.

The CMAI will be performed at Baseline (Day 1), and at Weeks 2, 4, 8, and 12 (EOS/ET).

#### Recording of CMAI Interviews

An in-study endpoint reliability program will be implemented. For the CMAI, caregiver interviews will be collected using digital recording equipment. [REDACTED] a company contracted by ACADIA, will collect and review the interviews to assess thoroughness of the interview and monitor the appropriate administration and scoring.

The rating scale assessments and recordings of the caregiver interviews will be sent in a secure manner for quality control, training, and calibration (standardization) purposes.

A unique subject number will be used to identify the recorded materials; subject identifying information will not be used. Qualified personnel from [REDACTED] responsible for reviewing the information may listen to these recordings. The recordings will be kept confidential and no other person will be allowed to listen to the recordings.

### **6.1.2 Zarit Burden Interview (ZBI)**

The ZBI was designed to assess the stresses experienced by caregivers of patients with dementia (Zarit et al. 1980; see [Appendix F](#)). The ZBI can be self-reported or administered as an interview. Caregivers are asked to respond to a series of 22 questions about the impact of the patient's disabilities on their life. For each item, caregivers are to indicate how often they felt that way (never, rarely, sometimes, quite frequently, or nearly always). The ZBI will be administered at Baseline (Day 1) and at Weeks 2, 4, 8, and 12 (EOS/ET).

Note: Professional caregivers do not complete this form.

### **6.1.3 Neuropsychiatric Inventory – Clinician Rating Scale (NPI-C)**

The NPI-C was developed to assess psychopathology in patients with dementia (de Medeiros et al. 2010; see [Appendix G](#)). The NPI-C evaluates NPS across many domains, as in the NPI (Cummings et al. 1994), as a standalone measure for specific NPS domains (e.g., dysphoria, agitation), or as a combination of both (presence of NPS across domains plus particular focus on one or more specific domains). The score of each item, if present, is clinically evaluated based on the symptom frequency, severity/intensity, and distress of a behavior. Multiple behaviors within a category are rated and included in the score. The NPI-C version of the NPI scale was designed to be administered by the clinician to the caregiver and can be administered to a professional caregiver or other involved person as long as they have detailed knowledge of the subject's behavior. If a subject is not able to provide reliable information (e.g., due to cognitive impairment, or is uncooperative), the NPI-C should be rated by the clinician using all other available information including behavioral observations.

The complete NPI-C, which includes agitation and aggression domains, will be administered by a qualified rater at Baseline (Day 1) and at Weeks 12 (EOS/ET) and the NPI-C agitation and aggression domains will be administered at Screening, and at Weeks 2, 4, and 8.

### **6.1.4 Mini–Mental State Examination (MMSE)**

The MMSE is a brief 30-point questionnaire that is used to quantitatively assess cognition (Folstein et al. 1975; see [Appendix H](#)). The MMSE includes simple questions and problems in a number of areas: the time and place of the test, repeating lists of words, arithmetic, language use and comprehension, and copying a drawing. It can be used to screen for cognitive impairment, to estimate the severity of cognitive impairment at a given point in time, to follow the course of cognitive changes in an individual over time, and to document an individual's response to treatment. The MMSE will be administered at Screening, Baseline (Day 1), and at Weeks 4, 8, and 12 (EOS/ET).

### **6.1.5 Modified Alzheimer's Disease Cooperative Study – Clinical Global Impression-Change (mADCS-CGIC)**

The mADCS-CGIC scale ([Schneider et al. 1997](#)) will be used to allow the Investigator to determine the subject's overall clinical condition as it relates to their symptoms of agitation and aggression, and to address the clinical significance of changes from Baseline in other psychometric measures ([Appendix I](#)). The mADCS-CGIC interview will be performed by the Investigator or a medically qualified rater. After completion of the interview, the rater will be asked to rate the subject's symptoms of agitation and aggression relative to the Baseline interview, using a standardized 7-point scale (1=marked improvement to 7=marked worsening).

The mADCS-CGIC will be administered at Baseline (Day 1) and at Weeks 2, 4, 8, and 12 (EOS/ET).

### **6.1.6 Karolinska Sleepiness Scale (KSS)**

The KSS is a self-reported subjective measure of a subject's level of drowsiness ([Akerstedt and Gillberg 1990](#); [Johns 2009](#); see [Appendix J](#)). With the modified version ([Geiger Brown et al. 2014](#)) respondents must choose which of 9 statements most accurately describes their level of sleepiness over a period of time, which for this study will be "on average over the previous week" (see Appendix J). The KSS will be administered at Baseline (Day 1) and at Weeks 2, 4, 8, and 12 (EOS/ET).

